## **3** STUDY OBJECTIVE(S) AND DESIGN

## 3.1 Study Objective(s)

Refer to the study protocol for a full list of study objectives.

Efficacy objective in the open label extension period is to determine the benefit of enzalutamide plus ADT as compared to placebo plus ADT as assessed by overall survival (OS). Additionally, time to new antineoplastic therapy will be summarized descriptively as supportive information in the evaluation of the overall survival endpoint.

Safety objective is to determine the safety of enzalutamide plus ADT as compared to placebo plus ADT.

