## 3.2 Study Design

This is a multinational phase 3, randomized, double-blind, placebo-controlled efficacy and safety study of enzalutamide plus ADT versus placebo plus ADT in patients with mHSPC. After the double-blind period has completed, eligible patients were allowed to received open label enzalutamide in an open label extension period.

Approximately 1100 subjects were randomized centrally 1:1, and the randomization was stratified by volume of disease (low versus high) and prior docetaxel therapy for prostate cancer (no prior docetaxel, 1-5 cycles, 6 cycles). High volume of disease is defined as metastases involving the viscera or, in the absence of visceral lesions, there must be 4 or more bone lesions, at least 1 of which must be in a bony structure beyond the vertebral column and pelvic bone. Prior docetaxel therapy is defined as 1 or more cycles of docetaxel but no more than 6 cycles.

In this study, patients received 4 capsules of enzalutamide (40 mg each) or placebo per day orally in the double-blind period. After the double-blind period has completed, eligible patients received 4 capsules of enzalutamide (40 mg each) in the open label extension period. As long as the patient is tolerating the study drug, the treatment should be continued until radiographic disease progression (rPD) or starting an investigational agent or new therapy for treatment of prostate cancer. Patients who discontinue study drug without radiographic progression will continue to follow the radiographic assessment schedule until radiographic progression event or until the target number of deaths is reached for the final analysis of OS.

The following assessments of prostate cancer status will be collected during OLE: soft tissue disease on CT scan or on MRI, bone disease on radionuclide bone scans, survival status, EQ-5D-5L, QLQ-PR25, FACT-P for QoL and BPI-SF for pain symptom assessment. Throughout the study, safety and tolerability were assessed by the recording of adverse events (AE), vital signs, physical examinations, 12-lead electrocardiograms (ECG), and safety laboratory evaluations (including PSA).

Patients will have a safety follow-up visit 30 days after their last dose of study drug or prior to initiation of new antineoplastic therapy for prostate cancer, whichever occurs first. All

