## 4 SAMPLE SIZE

For OS, 342 death events will be required to provide 80% power to detect a target HR of 0.73 with a target difference in Kaplan-Meier estimated median of approximately 15 months (40 months for placebo versus 55 months for enzalutamide) at the 4% significance level under the assumption of an exponential distribution. This significance level was chosen to apply a parallel testing strategy between OS and other key secondary endpoints (with allocated type I error rate of 1%) as described in section 7.4.1.

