#### 6.2 Time to Initiation of a New Antineoplastic Therapy

The initiation of a new antineoplastic therapy is based on the information collected in the (new) prostate cancer therapy CRF pages about all antineoplastic therapies, including cytotoxic and hormone therapies, initiated for prostate cancer subsequent to the study drug.

In patients with a new antineoplastic therapy initiated for prostate cancer, time to initiation of a new antineoplastic therapy (i.e., time to new antineoplastic therapy) is defined as the time interval from randomization to the date of first dose administration of the first antineoplastic therapy.

In patients with no new antineoplastic therapy initiated for prostate cancer, time to start of new antineoplastic therapy will be censored on the last visit date or the date of randomization, whichever occurs last.

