#### Figure 1 Testing Strategy for the Primary and Six Selected Secondary Endpoints

rPFS: radiographic progression-free survival; OS: overall survival; TTPP: time to PSA progression; TTNAnti: time to initiation of a new antineoplastic therapy; PSADecR: rate of PSA decline to <0.2 ng/mL; ORR: objective response rate; TTUri: the time to deterioration in urinary symptoms from the QLQ-PR25 \*OS will be tested at 0.05 only, if all other 5 secondary endpoints analyses are statistically significant at 0.01.

As the analysis for time to deterioration in urinary symptoms from the QLQ-PR25 was not significant, the final analysis of OS will be conducted at the level of significance of 0.04 (2-sided). The effect of Enzalutamide+ADT compared to placebo+ADT will be tested using a log-rank test stratified by prior docetaxel use (yes versus no) and disease volume (low versus high).

The null and alternative hypotheses to be tested are as follows:

The null hypothesis: OS for Placebo+ADT and Enzalutamide+ADT are not different The alternative hypothesis: OS for Placebo+ADT and Enzalutamide+ADT are different

The following SAS code will be used to compute the Kaplan-Meier estimates and curves, and the stratified log-rank test:

PROC LIFETEST DATA=INPUT ATRISK

```
PLOTS=SURVIVAL(CB)
OUTSURV=SURVPL
ALPHA=0.04
ALPHAQT=0.04 METHOD=KM;
TIME AVAL*CNSR(1);
STRATA STRATUM/ GROUP=TREATMENT;
RUN;
where INPUT is the input dataset
```

AVAL is the time to the event variable,

CNSR is 0 (patients with events) or 1 (patients without no event, i.e. patient censored) STRATUM is the stratification variable (volume of disease and prior docetaxel use) TREATMENT is the treatment variable

Kaplan-Meier methods will be used to estimate the distribution of OS events by treatment group. The median OS will be estimated using the corresponding 50th percentile of Kaplan-Meier estimates. A two-sided 95% confidence interval will be provided for this estimate by use of the Brookmeyer and Crowley method. The 25th percentile and the 75th percentile of OS will also be provided. A Kaplan-Meier plot by treatment group will be presented. The estimates of the event free rate on a 3-monthly basis up to 1 year and every 6 months thereafter will be summarized by treatment group, as long as at least 10 patients are at risk.

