#### 7.4.2 Time to Initiation of a New Antineoplastic Therapy

This will be analyzed using the same analysis methods as OS, but formal statistical test will not be conducted.

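### Kaplan-Meier for time to new antineoplastic therapy censors subjects who die untreated, so its event-free rates and median times understate, and one minus Kaplan-Meier overstates, actual subsequent therapy use

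*SAP*

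**What the plan says.** SAP 6.2 defines the event as the first dose of the first new antineoplastic therapy for prostate cancer. For subjects with none, "time to start of new antineoplastic therapy will be censored on the last visit date or the date of randomization", whichever is later. The rule makes no exception for death, so censoring of untreated deaths follows from it although the SAP does not say so.

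SAP 7.4.2 adds: "This will be analyzed using the same analysis methods as OS", with no formal test. The OS methods in SAP 7.4.1 are Kaplan-Meier curves by arm, the median and quartiles, a stratified Cox hazard ratio, and this set of rates: "The estimates of the event free rate on a 3-monthly basis up to 1 year and every 6 months thereafter", shown while at least 10 subjects remain at risk.

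SAP 3.1 gives the purpose: "time to new antineoplastic therapy will be summarized descriptively as supportive information in the evaluation of the overall survival endpoint".

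SAP 7.2.4 separately plans summaries of new prostate cancer therapies in the ITT population; these are not Kaplan-Meier estimates. Neither document plans a cumulative incidence function, another competing-risk method, or a composite with death for this endpoint. The main-study SAP, which this SAP supplements, is not among the documents.

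**The concern.** For OS, death is the event and Kaplan-Meier is the right estimator. For the start of new therapy, death makes the event impossible. Censoring at or before death assumes that the subject stays at the same future risk of starting therapy as those still alive and untreated. One minus Kaplan-Meier then describes therapy use in a setting where nobody dies, not the share of randomised subjects who actually started therapy.

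That share is what a reader needs here. The endpoint is kept to help interpret OS, that is, how much subsequent therapy each arm received and when. At the OS interim analysis there were 84 deaths (SAP 7.4.1), or 84/1100 = 7.6% of subjects, and the distortion was probably small. The final analysis comes at about 342 deaths, or 342/1100 = 31.1%, so death is no longer a rare competing event.

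**Working it through.** **Inputs from the plan.** SAP 4: "342 death events will be required to provide 80% power to detect a target HR of 0.73", with medians of "40 months for placebo versus 55 months for enzalutamide", exponential survival and a 4% significance level. SAP 3.2: "Approximately 1100 subjects were randomized centrally 1:1". SAP 7.4.1 makes the OS test 2-sided.

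**The plan's own figure.** With z = 2.0537 + 0.8416 = 2.8954 (2-sided 0.04, 80% power):
- Schoenfeld: 4z²/(ln 0.73)² = 338.6, so 339 deaths.
- Freedman: z² × (1.73/0.27)² = 344.2, so 345 deaths.
- Power with 342 deaths by Schoenfeld is 80.4%.

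The stated 342 reproduces, so the OS medians are a fair source of planned death rates. All-cause death hazards are ln 2/40 = 0.01733 and ln 2/55 = 0.01260 per month.

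**Assumptions, because the documents give no figures.** Median time to new therapy is 30 months (placebo) and 60 months (enzalutamide). The hazard of death before new therapy is 40% of the all-cause hazard in each arm. Hazards are constant. Untreated deaths are censored at death; the SAP censors at the last visit before it, a detail ignored here.

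**Formulas.** Let L be the hazard of starting therapy and M the hazard of death before therapy.
- One minus Kaplan-Meier: 1 − exp(−Lt).
- Cumulative incidence: [L/(L+M)] × [1 − exp(−(L+M)t)].

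Placebo: L = ln 2/30 = 0.02310, M = 0.4 × 0.01733 = 0.00693. Enzalutamide: L = ln 2/60 = 0.01155, M = 0.4 × 0.01260 = 0.00504.

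**Results.** The excess is taken from unrounded values.

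| Month | Placebo 1−KM | Placebo cum. inc. | Excess (points) | Enza 1−KM | Enza cum. inc. | Excess (points) |
|---|---|---|---|---|---|---|
| 24 | 42.6% | 39.5% | 3.1 | 24.2% | 22.9% | 1.3 |
| 36 | 56.5% | 50.8% | 5.6 | 34.0% | 31.3% | 2.7 |
| 48 | 67.0% | 58.7% | 8.3 | 42.6% | 38.2% | 4.3 |

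In the terms the SAP prints, the month-48 event-free rate is 33.0% rather than 41.3% for placebo, and 57.4% rather than 61.8% for enzalutamide. The between-arm gap at month 48 is 24.4 points rather than 20.5.

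**Median time.** Setting the cumulative incidence to 50% gives t = −ln[1 − 0.5(L+M)/L]/(L+M). This is about 35 months rather than 30 for placebo, and 76 rather than 60 for enzalutamide.

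**Sensitivity.** With a pre-therapy share of 25–60% and therapy medians of 30–90 months, the month-48 excess is 2.8–11.9 points for placebo and 2.1–9.0 for enzalutamide. Halving the share in the example to 20% gives 4.3 and 2.3 points.

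**Ordering of the arms.** If both arms have the same pre-therapy share, the excess was larger for placebo in every case tried (months 36–60, shares 25–100%, therapy medians 20–60 months placebo and 45–80 enzalutamide). With unequal shares it can reverse. Take therapy medians of 25 and 80 months, pre-therapy death hazards of 0.004 and 0.008 per month, and a death hazard after therapy of N = 0.03 in both arms. Total deaths are 1 − exp(−(L+M)t) − [L/(N−L−M)] × [exp(−(L+M)t) − exp(−Nt)]. At month 60 this gives 59.0% for placebo and 50.0% for enzalutamide, yet the excess is 6.7 points for placebo and 7.7 for enzalutamide.

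**The case against.** Four points can be made for leaving the plan alone.

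1. **Nothing is decided on this output.** It is descriptive, supportive and untested, and the Cox hazard ratio remains valid as a cause-specific hazard ratio. This stands and caps the severity.
2. **SAP 7.2.4 already tabulates new therapy in the ITT population.** That tabulation is not biased by the censoring rule, so it would be wrong to say that all reported therapy use is overstated. But it gives no estimates at set times and does not allow for unequal follow-up. It would sit beside Kaplan-Meier figures that disagree with it, unexplained.
3. **Month 48 flatters the size.** Under the planned hazards, 56% and 45% would be dead by then, whereas 342 of 1100 is 31%, a level reached at about 25 months of uniform follow-up. Deaths at the OS interim were 84 against about 170 expected (Protocol 7.4.2, OS), which may mean a lower death rate than planned, though the timing is not given. This is why months 24 and 36 are shown too. Later time points are still printed while 10 subjects remain at risk.
4. **A reader might infer that the overstatement must be larger in the arm with more deaths.** The documents do not support this. The excess depends on deaths before new therapy and on the rate of starting therapy. SAP 7.4.1 gives only total deaths (39 enzalutamide, 45 placebo), not split by prior new therapy, and the counterexample above shows the order can reverse.

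**Conclusion.** The point holds as a low-severity one. Within each arm the direction is certain as soon as anyone dies untreated: the event-free rates and median times are too low as descriptions of actual use, and one minus Kaplan-Meier is too high. The size rests on assumed therapy medians, an assumed share of deaths before therapy and constant hazards. In the illustration it runs from 1.3 to 3.1 points at month 24 and from 4.3 to 8.3 at month 48, and it shrinks if fewer subjects die before new therapy. The distortion can differ between arms, so the displayed gap may be off, but neither its size nor its sign can be fixed from the documents.

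**What to change.** In SAP 6.2 and 7.4.2:
- name death before new therapy as a competing event, using the death dates already derived for OS;
- add Aalen-Johansen cumulative incidence by arm at the time points already planned;
- report the number of deaths without new therapy by arm;
- label the stratified Cox hazard ratio cause-specific.

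Keep the Kaplan-Meier output alongside, for continuity with the primary analysis. The cost is a few lines of SAP text and code, one extra table or figure, and a footnote explaining why the two sets of estimates differ. No new data are needed, and neither alpha nor sample size changes.

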## 7.5 Analysis of Safety

All analysis of safety will be presented for Enzalutamide, Placebo and Placebo crossover group on the SAF, unless specified otherwise. All AEs will be listed.

#### 7.5.1 Adverse Events

The coding dictionary for this study will be MedDRA v23.0. Treatment-emergent AEs will be coded to SOC and preferred terms using MedDRA and graded using NCI-CTCAE v4.03.

Treatment-emergent AEs will be tabulated alphabetically by SOC and by preferred terms within SOC.

An overview table will include the following details for Enzalutamide, Placebo and Placebo crossover group:

- Number of TEAEs,
- Number and percentage of patients with TEAEs,
- Number of NCI-CTC grades 3 and 4 TEAEs,
- Number and percentage of patients with NCI-CTC grades 3 and 4 TEAEs,
- Number of drug related TEAEs,
- Number and percentage of patients with causally drug related TEAEs,
- Number of serious TEAEs,
- Number and percentage of patients with serious TEAEs,
- Number of serious drug related TEAEs,
- Number and percentage of patients with serious drug related TEAEs,
- Number of TEAEs leading to death,
- Number and percentage of patients with TEAEs leading to death,
- Number of drug related TEAEs leading to death,
- Number and percentage of patients with drug related TEAEs leading to death,
- Number of TEAEs leading to withdrawal of treatment,
- Number and percentage of patients with TEAEs leading to withdrawal of treatment,
- Number of drug related TEAEs leading to withdrawal of treatment,
- Number and percentage of patients with drug related TEAEs leading to withdrawal of treatment.
- Number of TEAEs leading to dose reduction,
- Number and percentage of patients with TEAEs leading to dose reduction,
- Number and percentage of death

The number and percentage of patients with TEAEs, as classified by SOC and preferred terms will be summarized for each treatment group. Summaries will be provided for:

- TEAEs
- NCI-CTC grade 3 or higher TEAEs

- drug related TEAEs,
- serious TEAEs,
- drug related serious TEAEs,
- TEAEs leading to withdrawal of treatment,
- drug related TEAEs leading to withdrawal of treatment,
- TEAEs leading to dose reduction,
- TEAEs leading to dose interruption,
- TEAEs, excluding serious AEs, that equal to or exceed a threshold of 5.0% in any treatment group,
- TEAEs leading to death,
- drug related TEAEs leading to death,

The number and percentage of patients with TEAEs, classified by preferred terms by decreasing frequency within the enzalutamide group will also be summarized.

The number and percentage of patients with TEAEs, as classified by SOC and preferred terms will also be summarized by maximum severity (reported according to NCI-CTCAE version 4.03).

In the patient count, if a patient has multiple TEAEs with the same SOC or PT, but with different severity, then the patient will be counted only once with the worst severity. However, if any of the severity values are missing then the patient will be counted only once with missing severity. In the AE count, the AEs will be presented in each category they were classified to. Summaries will be provided for:

- TEAEs by NCI- CTCAE
- drug related TEAEs by NCI- CTCAE,
- serious TEAEs by NCI- CTCAE

The number and percentage of patients with TEAEs that equal to or exceed a threshold of 5.0% in any treatment group, classified by preferred terms (by decreasing frequency within the enzalutamide group) will be summarized by treatment group and time interval. The percentage of patients are calculated based on the number of patients still on treatment at the time-point corresponding to the lower limit of the time intervals. Time intervals will be categorized according to the following categories:

- $\leq$ 3 months;
- >3 months to  $\leq 6$  months;
- >6 months to  $\leq 12$  months;
- >12 months to  $\leq$ 24 months;
- >24 months to  $\leq$ 36 months;
- >36 months.

To adjust for the treatment duration, the number of TEAEs per 100 patients-years will be summarized, as classified by SOC and PT, per treatment group and CTI-CTC grade (3-5 and total). The number of TEAEs per 100 patients-years is calculated as the number of events

\*100 / (sum of the treatment emergent period duration of all patients treated in the corresponding treatment group, in years).

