# 5.5.4 Criteria for Defining the Severity of an Adverse Event

AEs, including abnormal clinical laboratory values, will be graded using the NCI-CTCAE guidelines (version 4.03).

The items that are not stipulated in the NCI-CTCAE (version 4.03) will be assessed according to the criteria below and entered into the eCRF:

Grade	Assessment Standard
1-Mild	Asymptomatic, or mild symptoms, clinical or diagnostic observations noted; intervention not indicated.
2-Moderate	Local or noninvasive intervention indicated.
3-Severe	Medically significant but not immediately life threatening, hospitalization or prolonged hospitalization.
4-Life Threatening	Life threatening consequences, urgent intervention indicated
5-Death	Death related to AE

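### In the three maximum-severity adverse event tables, one ungraded record is enough to move a patient with a known grade 3 to 5 event to missing severity

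*SAP*

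**What the plan says.** SAP 7.5.1 plans patient counts by SOC and preferred term at each patient's maximum CTCAE grade. If a patient has several TEAEs in the same SOC or PT with different grades, "then the patient will be counted only once with the worst severity". The next sentence makes an exception: "However, if any of the severity values are missing then the patient will be counted only once with missing severity".

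The rule applies to the patient count in three summaries: "TEAEs by NCI- CTCAE", "drug related TEAEs by NCI- CTCAE", and serious TEAEs by grade. In the event count, each AE stays in its own category.

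The same section also plans a SOC and PT patient table of "NCI-CTC grade 3 or higher TEAEs", a table of TEAEs leading to death, and an overview with counts of patients with grade 3 and 4 events. The exception is not written for any of these.

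SAP 7.12.1 does not impute severity; its listed exceptions to the no-imputation principle are all dates. Protocol 7.5 plans worst toxicity grades per subject for selected AEs and laboratory analytes. Protocol 5.5.4 requires AEs to be graded by CTCAE version 4.03 and gives a fallback 1 to 5 scale for items that CTCAE does not cover.

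**The concern.** The exception is triggered by any missing grade, not by all grades being missing, and it exempts no known high grade. A patient with a recorded grade 4 event and one ungraded record in the same SOC leaves the grade 4 row. A patient with a recorded grade 5 event leaves the grade 5 row in the same way, although nothing on the scale is higher.

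A reader of these three tables could therefore see fewer patients at grade 3 to 5 than were recorded. The totals could also disagree with the grade 3 or higher table for the same SOC, and no footnote is planned to explain the difference.

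The chance of being moved rises with the number of records a patient has in a row, so it is larger by SOC than by PT and larger with longer observation. Under SAP 6.3 the enzalutamide group's treatment-emergent period continues through the open-label extension, while the placebo group's period ends no later than the start of open-label enzalutamide. Any loss could therefore fall more heavily on the enzalutamide group. The documents do not allow the size of that imbalance to be estimated.

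**Working it through.** The plan gives no figure to reproduce here, because the point concerns a counting rule. The check has two parts.

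**1. The rule applied literally.** For one patient's records in one SOC or PT:

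| Recorded grades | SAP rule | Worst recorded grade |
|---|---|---|
| 2, 3 | 3 | 3 |
| 3, missing | missing | 3 |
| 4, 1, missing | missing | 4 |
| 5, missing | missing | 5 |
| 1, missing | missing | 1 |
| missing only | missing | missing |

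In the second to fourth rows the patient is certainly at grade 3 or higher, yet the SAP rule shows none of them there. In the fourth row the maximum is known exactly. No set of records moves a patient into grades 3 to 5 under the SAP rule who would not be there under the worst recorded grade, so the counts at those grades cannot rise.

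**2. How often it could happen.** Let q be the chance that a record is ungraded, independently between records, and m the number of other records the patient has in the row. A patient with a known grade 3 to 5 event is moved with probability 1 − (1 − q)^m. The documents do not give q; 0.1% to 1% is assumed.

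| q | m = 1 | m = 4 | m = 9 |
|---|---|---|---|
| 0.1% | 0.10% | 0.40% | 0.90% |
| 0.5% | 0.50% | 1.99% | 4.41% |
| 1% | 1.00% | 3.94% | 8.65% |

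**Illustration.** SAP 7.5 states: "All analysis of safety will be presented for Enzalutamide, Placebo and Placebo crossover group on the SAF, unless specified otherwise". The planned 550 per arm (Protocol 7.1) stands in for the size of one group in the safety population. Assume 20 patients with a grade 3 to 5 event in a SOC row, each with 4 other records there. Before any move the row shows 20/550 = 3.636%.

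- q = 0.1%: expected moved 20 × 0.0040 = 0.080; (20 − 0.080)/550 = 3.622%.
- q = 0.5%: expected moved 20 × 0.0199 = 0.397; (20 − 0.397)/550 = 3.564%.
- q = 1%: expected moved 20 × 0.0394 = 0.788; (20 − 0.788)/550 = 3.493%.

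The denominator is held at 550. SAP 7.1 and 7.12 set a default denominator of patients with non-missing data. They do not say whether a patient counted as missing severity also leaves the denominator in these tables.

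**The case against.** The strongest case against acting is that the consequence may be nil. Protocol 5.5.4 gives every AE a grading scale, Protocol 8.1.1 makes sites responsible for complete data and queries, and a data review is planned before lock. Nothing in the documents suggests that ungraded records will exist. The size above rests on assumed inputs, and even at the upper assumed rate less than one of the 20 patients is expected to move. The 8.65% figure needs both that rate and nine other records in one row, so it is not typical.

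The information also survives elsewhere: in the grade 3 or higher and fatal TEAE tables, the event counts, the grade 3 to 5 rates per 100 patient-years and the AE listings. Moved patients remain visible under missing. All of this stands, and it limits the point to a minor one.

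The remaining argument is that this is a choice of convention: when a grade is missing the true maximum is unknown, and the SAP says so rather than printing a lower bound. That has force for a patient with grade 1 and a missing grade. It does not hold for grade 5, where the maximum is known. Nor does it justify taking a patient with a recorded grade 3 or 4 out of the grade 3 to 5 rows, because that patient is at grade 3 or higher whatever the missing value is.

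**Conclusion.** The concern holds and is minor. The wording is unambiguous, and no other part of the SAP repairs it. Confidence is high in the reading of the rule and in the direction of its effect. The size is uncertain because it depends on an assumed 0.1% to 1% of ungraded records, independence between records, and the assumed numbers of severe patients and records per patient. In the illustration 3.64% becomes 3.62% to 3.49%; with complete grading nothing changes. OS and the other safety outputs named above are not affected.

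**What to change.** Replace the exception in SAP 7.5.1 with: *A patient is shown at the highest grade recorded within the SOC or PT; the missing category is used only if no grade is recorded there for that patient.* Add a footnote to each of the three tables giving the number of patients with any ungraded TEAE. This covers the one weakness of the new rule: a patient with grade 1 and a missing grade would appear as grade 1, which may understate the true maximum.

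The cost is one sentence, the matching derivation in three tables and one footnote; no new data are needed. SAP Section 1 allows revisions before hard lock and otherwise asks for changes to be justified in the Clinical Study Report. This SAP supplements SAP version 3.0, which was not available for this review. If the primary-analysis tables used the present rule, the footnote should also state the change so that the two sets of double-blind results can be compared.

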#### 6.3 Treatment Emergent Adverse Event (TEAE)

A TEAE is defined as an AE that occurs or worsen at any time during the treatment emergent period. The treatment emergent period is time interval encompassing the double-blind treatment emergent period and the OLE treatment emergent period.

The double-blind treatment emergent period is defined as the time interval from the first double-blind study drug intake up to 30 days after the date of the last dose of double-blind study drug, study discontinuation, the start of new antineoplastic therapy, or the first dose of OLE treatment, whichever occurs first.

If AE start date is the same date as the study start, then it will be considered as a TEAE if the box 'Onset after first dose of study' is ticked in the Electronic case report form(eCRF). If a patient experiences an event both during the pre-investigational period and during the investigational period, the event will be considered as TEAE only if it has worsened in severity (i.e. it is reported with a new start date).

The OLE treatment emergent period is defined as the time interval from the OLE study drug intake up to 30 days after the date of the last dose of OLE study drug, study discontinuation, or the start of new antineoplastic therapy, whichever occurs first.

AE with both a missing start and stop dates, and AEs with a missing start date but has a known stop date which is on or after the first dose of study drug will be considered treatment-emergent.

For each treatment group, the treatment emergent period is as follows;

- Enzalutamide group: from the first DBT study drug intake up to 30 days after the date of the last dose of study drug, study discontinuation, or the start of new antineoplastic therapy, whichever occurs first.
- Placebo group: from the first DBT study drug intake up to 30 days after the date of the last dose of placebo, start of open-label enzalutamide, study discontinuation, or the start of new antineoplastic therapy, whichever occurs first.
- Placebo crossover group: from the first OLE study drug intake up to 30 days after the date of the last dose of OLE study drug, study discontinuation, or the start of new antineoplastic therapy, whichever occurs first.

AEs will be coded to System Organ Class (SOC) and preferred term using MedDRA v23.0 and severity graded using National Cancer Institute's Common Terminology Criteria version 4.03 (NCI-CTCAE v4.03) for AEs.

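### The adverse event rates per 100 patient-years set enzalutamide over blinded plus open-label time beside placebo over time before crossover only, so they adjust for duration only if the event rate is constant

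*SAP*

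**What the plan says.** SAP 7.5.1 introduces the rate with the words "To adjust for the treatment duration, the number of TEAEs per 100 patients-years will be summarized", by system organ class and preferred term, for each group, in total and for grades 3-5. The denominator is the "sum of the treatment emergent period duration of all patients treated in the corresponding treatment group, in years".

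SAP 6.3 describes the overall treatment-emergent period as a "time interval encompassing the double-blind treatment emergent period and the OLE treatment emergent period", then sets a different window for each group:

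- "Enzalutamide group: from the first DBT study drug intake up to 30 days after the date of the last dose of study drug", or study discontinuation or new antineoplastic therapy if earlier. There is no cut at the start of the extension.
- Placebo: up to 30 days after the last placebo dose, with earlier stops that include crossover: "the date of the last dose of placebo, start of open-label enzalutamide, study discontinuation, or the start of new antineoplastic therapy".
- "Placebo crossover group: from the first OLE study drug intake up to 30 days after the date of the last dose of OLE study drug", with the same two earlier stops.

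SAP 7.5 tabulates the three groups together unless otherwise specified. SAP 3.1 gives a comparative aim: "Safety objective is to determine the safety of enzalutamide plus ADT as compared to placebo plus ADT".

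SAP 6.3 also defines a double-blind treatment-emergent period that ends at the first open-label dose. No table in SAP 7.5 restricts both randomized arms to it.

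**The concern.** A single rate per 100 patient-years averages the event rate over whatever time is counted. If the counted spans differ between arms and the event rate changes with time since first dose, the averages differ even when the drug does nothing.

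The extra enzalutamide time is not exchangeable with the placebo time. It is later and unblinded. It also comes from subjects who, under Protocol 12.6.3, had met none of the discontinuation criteria, and Protocol 6.1 lists intolerable adverse events among those criteria.

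The direction depends on the event. Events clustered after the start of treatment are diluted on enzalutamide, which can mask an early excess. Events that become more frequent with time give an apparent excess on enzalutamide that reflects only longer observation. Rates of this kind carry weight in the safety argument: Protocol 1.3 uses event rates per 100 patient-years to single out fall and hypertension, and relies on duration-adjusted rates for grade 3 or higher and serious events.

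**Working it through.** **What the documents give.** They state no exposure-adjusted rate, so there is no figure to reproduce. The event counts used below for timing do reproduce. The Schoenfeld formula gives 263 events for HR 0.67, two-sided 0.05 and 90% power (stated: 262). It gives 339 for HR 0.73, 0.04 and 80% power (stated: 342), and power at 342 events is 80.4%.

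**Assumptions, not in the documents.** Both arms have the same event rate at every time since first dose (no drug effect). Time on drug is exponential with the planned rPFS medians from Protocol 7.1 (20 months placebo, 30 months enzalutamide). All subjects have a common follow-up, and the 30-day tail is ignored. The event-rate shapes are hypothetical.

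**Follow-up.**

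- Blinded: solve 550(1 - e^(-t ln2/20)) + 550(1 - e^(-t ln2/30)) = 262, giving t = 9.5 months. An alternative of 14 months was also tried.
- Final, from the OS medians in SAP 4 (40 and 55 months): solve 550(1 - e^(-t ln2/40)) + 550(1 - e^(-t ln2/55)) = 342, giving t = 25 months.
- Final, extrapolated from the 84 deaths in SAP 7.4.1 at a constant hazard: 9.47 × ln(1 - 342/1100) / ln(1 - 84/1100) = 44 months.

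**Mean counted time**, (1 - e^(-λT))/λ with λ = ln2/median: placebo 8.1 months (11.1 with 14-month blinded follow-up); enzalutamide 19.0 or 27.8 months.

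**Worked case.** The rate is 60 per 100 patient-years for 3 months, then 10. Mean time within the first 3 months is 2.849 months on placebo and 2.898 on enzalutamide.

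- Placebo: 10 + 50 × 2.849/8.074, about 27.6.
- Enzalutamide to 25 months: 10 + 50 × 2.898/18.99 = 17.6, ratio 0.64.
- Enzalutamide to 44 months: 10 + 50 × 2.898/27.77 = 15.2, ratio 0.55.

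**All shapes, 9.5 months blinded, final follow-up 25 / 44 months:**

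| True rate per 100 PY, both arms | Placebo | Enzalutamide as planned | Ratio as planned | Ratio, both arms blinded only |
|---|---|---|---|---|
| 10 throughout | 10.00 | 10.00 / 10.00 | 1.00 / 1.00 | 1.00 |
| 60 for 3 months, then 10 | 27.65 | 17.63 / 15.22 | 0.64 / 0.55 | 0.98 |
| 20 for 6 months, then 10 | 16.71 | 12.95 / 12.02 | 0.78 / 0.72 | 0.99 |
| 2 in year 1, then 4 | 2.00 | 2.90 / 3.25 | 1.45 / 1.62 | 1.00 |
| 2 in year 1, then 6 | 2.00 | 3.79 / 4.49 | 1.90 / 2.25 | 1.00 |

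With 14 months of blinded follow-up, the planned ratios for the four non-constant rows are 0.77 / 0.67, 0.87 / 0.81, 1.30 / 1.46 and 1.54 / 1.83. The blinded-only ratios are 0.97 to 1.01.

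**A second set of assumptions.** A simulation used median times to discontinuation of 14-20 months (placebo) and 30-40 months (enzalutamide), extension start spread over 8-28 or 12-34 months, and cut-off at about 40-48 months. Mean exposure was 12-16 and 26-32 months.

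- 60 per 100 patient-years for 6 months, then 20: planned ratio 0.71-0.84.
- 20, doubling after month 24: planned ratio 1.22-1.38.
- Both arms cut at extension start: 0.91-0.97 and 1.00-1.03.

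The cut removes most of the artefact. Some remains for early events because blinded exposure also differs between arms.

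**The case against.** The strongest reply is that SAP 7.5.1 already compares the arms at like time since first dose. Just before the rate, it plans a table over six intervals, from the first 3 months to beyond 36 months, whose denominator is the patients still on treatment when each interval opens. Late enzalutamide time cannot dilute its early intervals. This stands for TEAEs reaching 5% in any group. It gives patient percentages rather than rates, however, and it leaves out rarer events. The AESI overview is neither split by time nor adjusted for exposure.

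Second, SAP 1 calls this document a supplement to the main-study SAP. Version 3.0 is not supplied and may contain a blinded comparison at the rPFS cut-off. This also stands. Such a comparison would not change the side-by-side rates planned here, nor cover blinded time between that cut-off and crossover.

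Third, the tables are descriptive, Protocol 12.6.7 itself asks for a combined blinded and open-label enzalutamide summary, and SAP 7.3.1 tabulates exposure by group, so the imbalance will be visible. That is fair, and it limits the weight of the point. But the protocol does not ask for the combined summary to be set against blinded placebo, and seeing unequal exposure does not tell a reader how far a given rate has moved.

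A reader might infer that the trial has no valid safety comparison between arms, or that this rate is the only account taken of time on treatment. The interval table contradicts the second inference, and the absence of version 3.0 prevents the first.

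**Conclusion.** The point holds in a limited form. The mismatch of windows follows from SAP 6.3 and 7.5.1 without any assumption: the rate labelled as the duration adjustment does that job only under a constant event rate. TEAEs below 5% are left to this pooled rate and to crude percentages that do not account for time, and the AESI overview has no protection either.

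The size is not known. The illustrative null ratios, about 0.55-0.87 for early-onset events and 1.2-2.3 for late-rising events, rest on assumed exposures, follow-up and rate shapes. With a constant rate the ratio is 1.00. A reader should not conclude that enzalutamide harm is in fact being hidden or exaggerated; the documents give neither the exposures nor the event timing needed to say so. No formal safety test is affected.

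**What to change.** In SAP 7.5.1, for all TEAEs and for the AESIs:

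1. Add Enzalutamide versus Placebo rates per 100 patient-years, and percentages, with both arms restricted to the double-blind treatment-emergent period defined in 6.3.
2. Add rates by the time-since-first-dose intervals already listed in 7.5.1, to deal with the remaining difference in blinded exposure.
3. Keep the combined blinded plus open-label enzalutamide rate as a descriptive column, labelled as not directly comparable with placebo.

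No new data are needed, since the period and the intervals are already defined. The cost is an additional set of tables that partly repeats the primary report, with late intervals likely to hold little placebo time.
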